7.1.2 Alzheimer’s Disease Cooperative Study–Activities of Daily Living (ADCS-ADL)

The ADCS-ADL comprises 23 questions covering a wide array of activities of daily living. Many of the activities begin with an assessment of whether that activity is relevant and then, if yes, follow with an assessment of the difficulty. The total score over all activities ranges from 0-78 where a higher score indicates more autonomy (better outcome).

	Title: Statistical Analysis Plan
	Project #: IG1002 AMBAR
	Version: Final 1.0 Effective Date: 31July2018
	Protocol Version: Version 5.0 Effective Date: Feb2018

The total score is analyzed as a continuous variable, and will be summarized at each time point.

The total ADCS-ADL score at 14 months is the end point for the primary efficacy analysis. The other point in time will be regarded as secondary end points.

7.1.3 Mini-Mental Status Examination (MMSE)

The MMSE is a brief 30-point questionnaire test that is used to screen for cognitive impairment, where 30 is the best possible score and lower scores indicate cognitive impairment. The MMSE inclusion criterion for this study is between 18 and 26 (both inclusive).

The score is analyzed as a continuous variable, and will be summarized at each time point.

7.1.4 Neuropsychological Specific Battery (NPSB)

The NPSB has a several components which are described separately below.

7.1.4.1 Rey Auditory Verbal Learning (RAVLT)

The RAVLT has 5 scores of immediate recall of a single list (A), followed immediately by recall of words off a different list (B) and then recall of the first list (short-delay). After 30 minutes recall from the first list is assessed (long-delay). The test ends with a test of recognition of the list ‘A’ words. Each of these tests results in a score between 0 and 15, where higher score indicates better recall. A total score will be calculated as sum of the 5 scores.

The total score and all sub-scores are analyzed as continuous variables, and will be summarized at each time point.

7.1.4.2 NAB Naming Test

The NAB Naming test assesses each subject’s ability to name 31 common objects. They are provided with a semantic and then a phonemic cue as needed. The total score ranges from 0 (no objects are named) to 31 (all objects are named).

The total score is analyzed as a continuous variable, and will be summarized at each time point.

	Title: Statistical Analysis Plan
	Project #: IG1002 AMBAR
	Version: Final 1.0 Effective Date: 31July2018
	Protocol Version: Version 5.0 Effective Date: Feb2018

7.1.4.3 Symbol Digit Modalities Test (SDMT)

The SDMT assesses each subject’s ability to substitute specific numbers for specific symbols after being provided a map. They are asked to map as many symbols to numbers as possible in 90 seconds. The score is the total number of correct numbers and can range from 0 (no correct matches) to 110, where higher scores indicate better performance.

The total score is analyzed as a continuous variable, and will be summarized at each time point.

7.1.4.4 Phonetic and Semantic Verbal Fluency

The phonetic verbal fluency tests assess each subject’s ability to come up with lists of words beginning a specific letter. They are asked to come up with words that begin with ‘F’, ‘A’ and ‘S’. There is no upper limit, but more words indicate better fluency. The total number of words combined over the three lists is calculated for a total fluency score. The semantic verbal fluency test asks subject to name as many animals as possible, and more animals indicate better fluency.

All scores are analyzed as continuous variables, and will be summarized at each time point.

7.1.4.5 Cornell Scale for Depression on Dementia (CSDD)

The CSDD scores the rater’s opinion of the subject’s level of depression. The scores range from 0 to 38 where higher scores indicate more severe depression.

The total score is analyzed as a continuous variable, and will be summarized at each time point.

7.1.5 Neuropsychiatric Inventory Questions (NPI)

The NPI is a questionnaire covering many neuropsychiatric domains resulting in 2 total scores. The 10 item scoring will be calculated meaning that the two neurovegetative items (sleep and night-time behavior disorders; appetite and eating changes) are not included. The total score for frequency per severity ranges is calculated by multiplying the frequency (1 to 4) by the severity (1 to 3) for each domain (1 to 12) and summing over the 10 domains for a total range of 10 to 120. The total distress score (as rated by the caregiver) sums the distress score (0 to 5) over the 10 domains and ranges from 0 to 50. For both scores, a higher score indicates more impairment.

	Title: Statistical Analysis Plan
	Project #: IG1002 AMBAR
	Version: Final 1.0 Effective Date: 31July2018
	Protocol Version: Version 5.0 Effective Date: Feb2018

Both scores are analyzed as continuous variables, and will be summarized at each time point.

7.1.6 Clinical Dementia Rating (CDR-Sb)

The CDR-Sb assesses 6 different domains of dementia: memory, orientation, judgment and problem solving, community affairs, home and hobbies, and personal care. Each domain (other than personal care) is given a score of 0, 0.5, 1, 2 or 3, where higher scores indicate more severe dementia. The personal care domain is scored as 0, 1, 2 or 3, where higher scores indicate more severe dementia.

Each domain is analyzed as a categorical variable, and will be summarized at each time point.

7.1.7 Alzheimer’s Disease Cooperative Study-Clinical Global Impression of Change (ADCS-CGIC)

[figure not shown]
The ADCS-CGIC is a single ordinal assessment of the change in each subject’s condition compared to baseline. The potential responses are: Marked improvement (1), moderate improvement (2), minimal improvement (3), no change (4), minimal worsening (5), moderate worsening (6), and marked worsening (7).

The ADCS-CGIC will be summarized as a categorical variable at each time point.

7.1.8 Columbia-Suicide Severity Rating Scale (CSSRS)

The CSSRS assesses suicidal ideation, intensity of ideation, and suicidal behavior. For actual attempts, actual lethality and potential lethality are also assessed. Suicidal ideation assesses 5 types of ideation of increasing severity; intensity of ideation measures the intensity of the most severe ideation. Suicidal behavior examines 5 types of behavior. Actual lethality is scored for the most recent, most lethal, and initial actual attempts (range from 0 to 5). If actual lethality is scored as 0 then potential lethality is scored for the most recent, most lethal, and initial actual attempts (range from 0 to 2). For all scales, higher scores indicate more suicidal behavior.

To assess efficacy and changes from baseline the developers recommend analysis of change in suicidal ideation severity (0 to 5). This score is analyzed as a categorical variable, and will be summarized at each time point. The other scores can be analyzed in a similar manner, if indicated.

	Title: Statistical Analysis Plan
	Project #: IG1002 AMBAR
	Version: Final 1.0 Effective Date: 31July2018
	Protocol Version: Version 5.0 Effective Date: Feb2018

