6.1.2 Secondary Efficacy Variables

- a) Change from baseline in the cognitive, functional and neuropsychiatric scores and overall development as measured by MMSE, NPS battery, NPI, CDR-Sb, ADCS-CGIC, CSDD and C-SSRS. (6 measurements: week -3, -2 or -1 and 7-8; months 6, 9, 12 and 14) and QoL-AD, RUD-Lite[®] (5 measurements: weeks -3, -2 or -1; months 6, 9, 12 and 14). Moreover the optional questionnaires like OAS and ABS could be used at any visit in case any sign of aggression or restlessness.
- b) Variation in levels of A β ₁₋₄₀ and A β ₁₋₄₂ in CSF in the period between baseline lumbar puncture (before the start of the Intensive treatment period) and lumbar puncture immediately after the end of the last low-volume plasmapheresis (whenever this may be)
- c) Variation in the levels of A β ₁₋₄₀ and A β ₁₋₄₂ in CSF between the finalization and beginning of each of the 2 treatment periods.
- d) Levels of A β ₁₋₄₀, A β ₁₋₄₂, T-tau and P-tau in CSF throughout the study.

- e) Plasma levels of A β ₁₋₄₀ and A β ₁₋₄₂ before and after each plasma exchange for both treatment periods.
- f) Structural changes in volume of the hippocampus, posterior cingulate area, and other associated areas by MRI. Five measurements will be made (weeks -3, -2 or -1 and 7-8; months 6, 9 and 14).
- g) Variation in FDG-PET patterns (4 measurements: weeks -3, -2 or -1 and 7-8; months 9 and 14).

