Measurement of restlessness: Agitated Behavior Scale (ABS)⁵⁰. This includes 14 items grouped into three factors (disinhibition, and liability). The global score is obtained from the sum of the scores assigned to the different items. Increased severity is associated with higher scores.

Columbia-Suicide Severity Rating Scale (C-SSRS):

The scale is currently being used in a variety of settings from clinical trials to clinical practice. The Columbia–Suicide Severity Rating Scale (C-SSRS) was designed to quantify the severity of suicidal ideation and behaviour.

The primary outcomes to evaluate are: suicidal behaviour categorical rating, suicidal ideation categorical rating and to estimate the rate of suicidality.

We are going to use two versions of the scale that are currently being used in clinical trials:

- The **Baseline** version of the scale assesses lifetime suicidal ideation and behavior. This version is suitable as part of a patient's *first* interview in a private practice or as part of a clinical study.

- The **Since Last Visit** version of the scale assesses suicidality since the patient's last visit. This version is meant to assess patients who have completed at least one initial C-SSRS assessment, and should be used in every subsequent visit. The 'Since Last Visit' version of the C-SSRS is asking about any suicidal thoughts or behaviors the patient/participant may have had since the last time you have administered the C-SSRS.

Quality of Life AD Measure (QoL-AD):

The QoL-AD is a brief, 13-item measure designed specifically to obtain a rating of the patient's Quality of Life from both the patient and the caregiver. It was developed for individuals with dementia, based on patient, caregiver, and expert input, to maximize construct validity, and to ensure that the measure focuses on quality of life domains thought to be important in cognitively impaired older adults. It uses simple and straightforward language and responses & includes assessments of the individual's relationships with friends and family, concerns about finances, physical condition, mood, and an overall assessment of life quality.

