Clinical Dementia Rating CDR-Sb (6 domains)	FAS	CMH test (values on time point)		Excluded	Secondary analysis of cognitive impairment
ADCS –CGIC (1 score)	FAS	CHM test (values on time point)		Excluded	Secondary analysis of cognitive impairment
C-SSRS, suicidal ideation severity (1 score)	FAS	CHM test (values on time point)	Treatment/Bsl/Age /AD Severity	Excluded	Secondary analysis of cognitive impairment
QoL-AD (2 scores)	FAS	ANCOVA	Treatment/Bsl/Age /AD Severity	Excluded	Secondary analysis of cognitive impairment
RUD lite	FAS	Summary statistics for individual items			Descriptive analysis for resource consumptions.
Biomarkers at Time Points	FAS	ANCOVA	Treatment/Bsl/Age /AD Severity	Excluded	Biomarkers as secondary end points.

	Title: Statistical Analysis Plan
	Project #: IG1002 AMBAR
	Version: Final 1.0 Effective Date: 31July2018
	Protocol Version: Version 5.0 Effective Date: Feb2018

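### The SAP commits to only one of the three C-SSRS outcomes named in the protocol: suicidal behaviour and the rate of suicidality have no planned output, and the descriptive change score compares unlike recall periods

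*SAP*

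**What the plan says.** Protocol 7.2 describes the C-SSRS as a scale that "was designed to quantify the severity of suicidal ideation and behaviour" and states what is wanted from it: "The primary outcomes to evaluate are: suicidal behaviour categorical rating, suicidal ideation categorical rating and to estimate the rate of suicidality". These are primary outcomes of the scale. The trial's own co-primary endpoints are ADAS-Cog and ADCS-ADL. Two forms are used. The baseline "version of the scale assesses lifetime suicidal ideation and behavior", while the follow-up form asks only about the period since the scale was last given. Protocol 6.1.2 places the scale among the secondary efficacy variables, as change from baseline "as measured by MMSE, NPS battery, NPI, CDR-Sb, ADCS-CGIC, CSDD and C-SSRS", and 8.2 does the same.

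SAP 7.1.8 describes ideation, intensity, behaviour and lethality. It then says that, for efficacy and change from baseline, "the developers recommend analysis of change in suicidal ideation severity (0 to 5"), and of that score: "This score is analyzed as a categorical variable, and will be summarized at each time point". Everything else is covered by "The other scores can be analyzed in a similar manner, if indicated". The corresponding row in SAP 9.2.5 is "C-SSRS, suicidal ideation severity (1 score"), on the full analysis set, with a CMH test on visit values.

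**The concern.** The C-SSRS is the instrument in this trial that asks directly about suicidal thoughts and acts. If the SAP is followed as written, the report can be complete without showing how many patients in each arm had suicidal behaviour, or how many had any suicidality at all. Whether those outputs appear depends on a condition the SAP does not define. Because unblinding and final analysis both follow database lock (SAP 3), that condition could be judged with arm results in view.

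There is also a question of meaning. A change score that subtracts a lifetime assessment from one covering a few weeks or months does not measure change in the patient's state.

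**Working it through.** No power, alpha or event figure is involved, so the check sets the documents side by side.

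**Step 1. Outcomes named against outputs committed.**

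| C-SSRS outcome in protocol 7.2 | Committed output in the SAP |
|---|---|
| Ideation rating | Severity 0 to 5, frequency table and CMH test at each visit (7.1.8, 9.1.2, 9.2.5) |
| Behaviour rating | None; optional in 7.1.8, absent from 9.2.5 |
| Rate of suicidality | None; not mentioned anywhere in the SAP |

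One of three is covered, and 3 − 1 = 2 are not. A rate would be a binary per-patient summary, and SAP 9.1.3 says that binary analyses do not apply. SAP 7.2, which holds the safety endpoints, has subsections for the two agitation and aggression scales (OAS and ABS) but none for the C-SSRS.

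**Step 2. What the one planned analysis can show.** SAP 7.1.8 treats ideation (five types of increasing severity) and behaviour (five types) as separate parts of the scale. The planned score uses only the first part. A patient with a behaviour item endorsed and no ideation item endorsed therefore scores 0, the same as a patient with neither.

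**Step 3. Which forms enter.** SAP 7 slots efficacy assessments to visits and, where two fall in one window, keeps the one nearest the target day. Each follow-up form covers only its own interval, so a form that is not selected takes its interval out of the by-visit table. By contrast, SAP 7 includes unscheduled and early-termination values in its summaries of clinically significant abnormal values.

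**Step 4. Change from baseline.** SAP 7 promises summaries of change at each time point, 7.1 lists the C-SSRS among the change-from-baseline variables, and 7.1.8 cites change in ideation severity. Assume that the score is the most severe type endorsed over the form's recall period. A patient with lifetime severity 3 and severity 1 both at entry and at follow-up then gets 1 − 3 = −2, an apparent improvement with no change in state. A patient with lifetime severity 4 who had no current ideation at entry and develops severity 2 on study gets 2 − 4 = −2, although the patient has worsened. A positive change requires the patient to exceed the lifetime worst. The lean towards improvement applies in every arm.

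**Step 5. Does this reach the between-arm test?** No. SAP 9.1.2 applies the CMH test to actual visit values, and 9.2.5 repeats this for the C-SSRS row. That row also lists baseline, age and AD severity, without saying how they would enter. Even if lifetime history were used for adjustment, it would be a pre-treatment covariate and not a quantity subtracted from the outcome.

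**The case against.** The strongest reply is that the SAP does not exclude the other scores. It describes behaviour and lethality and permits their analysis, and SAP 7 has a general statement about summarising each variable whenever it is measured. That is correct, and it means the outputs are uncommitted, not forbidden. But the specific optional wording in 7.1.8 governs this scale, and neither text mentions a rate of suicidality.

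Several stronger readings are tempting, and the documents do not support them:

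- **That a suicidal act could surface only through spontaneous reports.** Protocol 9.1.1 also collects adverse events by clinical observation, laboratory analyses and open questioning. An act meeting the seriousness definition must be reported within 24 hours (9.2) and would appear in the SAE tables and listings (SAP 7.2.2). The monitoring committee sees unblinded event rates by arm (protocol 12.4). These routes do not supply the C-SSRS behaviour categories, but they do mean that behaviour is not hidden.
- **That the SAP misfiled the scale under efficacy.** The placement follows protocol 6.1.2 and 8.2, and protocol 6.1.3 and 8.3 do not list the scale under safety.
- **That the change score biases the treatment comparison.** The lean is common to all arms and the planned test does not use change.
- **That the cognitive-impairment comment in 9.2.5 has analytic meaning.** The same comment stands against NPI, CDR-Sb, ADCS-CGIC and QoL-AD. It is clerical.
- **That the visit-wise tests have almost no power.** This needs an event rate, and the documents give none. If events are rare, the table proposed below would be sparse too. Its value lies in complete description.

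**Conclusion.** The point stands in limited form. Two of the three C-SSRS outcomes named in protocol 7.2 have no committed output, and the single planned score cannot register behaviour without endorsed ideation. The change-from-baseline summary is not interpretable as change, but this harms only the descriptive tables. Neither co-primary analysis is touched.

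How many patients the gap would affect cannot be stated from the documents. The conclusion about behaviour assumes only that the two parts of the scale are scored separately, as SAP 7.1.8 describes. The conclusion about change rests on the recall periods in protocol 7.2 and on the scoring assumption in step 4. The change is worth making before lock: the protocol already asks for these outcomes, and the remedy is cheap.

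**What to change.** In SAP 7.1.8 and 9.2.5:

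1. Commit to a table giving, for each arm, the number and percentage of patients with any post-baseline suicidal ideation (1 to 5), any suicidal behaviour, and either.
2. Build it from all Since Last Visit forms, whether scheduled, unscheduled or early termination, without slotting.
3. Show lifetime history from the baseline form separately, or as a shift table.
4. Add a patient listing.
5. Drop the C-SSRS change-from-baseline summary, and remove the open condition on the other scores or define it.

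The table can be run on the safety set (SAP 5.3) without reclassifying the scale. Moving the C-SSRS formally to the safety endpoints is optional and would need alignment with protocol 6.1.2 and 8.2. The cost is SAP wording, one table and one listing. No new data are needed.

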7.1.9 Quality of Life- Alzheimer’s Disease (QoL-AD)

The QoL-AD has both a rating by a family member or caregiver and also a score by the subject. Each score ranges from 13 to 52, where higher scores indicate better quality of life.

Both scores are analyzed as continuous variables, and will be summarized at each time point.

7.1.10 Resource Utilization in Dementia (RUD) Lite Questionnaire

The RUD questionnaire will be analyzed in a descriptive manner. No cost will be calculated. Description of primary caregiver (Age, sex, relationship to patient, Number of children currently living with caregiver, living with patient, number of other caregivers involved, and contribution of primary caregiver among all caregivers) caregiver time, caregiver working status, patient living accommodation, and patient health care resource utilizations (hospitalizations, emergency room visits) and other services (district nurse, home aid/orderly, food delivery, day care, transportation, etc.) will be summarized by descriptive statistics for all assessments where the RUD is applied.

7.1.11 Biomarkers in Plasma and in the CSF

Aβ₁₋₄₀ and Aβ₁₋₄₂, T-tau, and P-tau in CSF and Aβ₁₋₄₀ and Aβ₁₋₄₂ in plasma are secondary efficacy parameter. The analysis of these biomarkers is described in Section 7.3.1.

7.2 SAFETY END POINTS

The primary criterion of safety will be the percentage of plasma exchanges (full and low volume exchanges, including the infusion of albumin and IVIG) associated with at least one adverse event that may be related to the study procedure (adverse reactions). In addition, consideration globally will be made of the percentage plasma exchanges (full and low-volume exchanges, including the infusion of albumin and IVIG) involving some adverse event, whether or not related to the procedure.

Vital signs (blood pressure, heart rate, respiration rate, and body temperature) will be recorded before, during and after each plasma exchange session, where required. Evaluation will also be made (where required) of the different laboratory test parameters (blood cell counts, platelet count, prothrombin time (Quick), fibrinogen, total proteins, and calcium).

During the treatment periods (before each plasma exchange) and on the days when there is no replacement, anxiety and restlessness tests will be made based on the Overt

	Title: Statistical Analysis Plan
	Project #: IG1002 AMBAR
	Version: Final 1.0 Effective Date: 31July2018
	Protocol Version: Version 5.0 Effective Date: Feb2018

Aggression Scale (OAS) and the Agitated Behavior Scale (ABS), whenever considered opportune.

According to the criterion of the investigator, all the clinically important changes in vital function, laboratory test parameters and neuroimaging findings will be evaluated. Any adverse events occurring following start of treatment will be counted as treatment emergent.

The analysis of tolerability will be based on description of the safety variables according to their nature.

The adverse reactions will be coded according to the adverse events classification of the World Health Organization (WHO) (MedDRA current version), and will be described by a synonym (Preferred Term) and the affected organ / system, the intensity, causality and seriousness.

The safety population will be used for all safety summaries unless otherwise noted. Summaries will be presented by treatment group and overall unless otherwise noted.

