10.3 Evaluation of Tolerability

The analysis of tolerability will be based on description of the safety variables according to their nature. In addition, a comparison of Adverse Drug Reactions between the treatment and the control groups will be performed.

The adverse reactions will be coded according to the adverse events classification of the World Health Organization (WHO) (MedRA current version), and will be described by a synonym (Lowest Level Term) and the affected organ / system, the intensity, causality and seriousness.

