5.3 SAFETY ANALYSIS SET

All patients included in the study and subjected to at least one plasma exchange session will form part of the safety population.

Control group subjects will also be included (without the plasma exchange) if they attended at least 1 of the 6 intensive treatment phase visits. For the control group from protocol version 1, patients will be included in the safety population if they have at least the intermediate visit performed.

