6 STUDY POPULATION SUMMARY

The set of FAS patients set will be used for all study population summaries unless otherwise noted. Summaries will be presented by treatment group and overall unless otherwise noted. The 3 combined active treatment groups will also be presented for the patient disposition, demographics and the medical history.

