7.2.2 Adverse Events

All adverse events will be coded using the Medical Dictionary for Regulatory Activities (MedDRA). Summaries will be presented for all adverse events (overall and by severity), adverse events determined by the investigator to be treatment-related (overall and by severity), serious adverse events, and adverse events causing discontinuation from the study.

The incidence of adverse events will be summarized using descriptive statistics by system organ class and preferred term. Patients are counted only once in each system organ class category, and only once in each preferred term category. Treatment-related adverse event summaries will include adverse events with missing relationship to study drug. For the summaries by severity, patients are counted at the greatest severity. Adverse events missing the flag indicating serious will be excluded from the summary of serious adverse events. In summary tables, AEs will be counted as “Not Related” if the causality with the product was recorded as “Unrelated”; Events will be counted as “Related” if the causality with the product was recorded as “Possibly”, or “Probably,” or “Unlikely”, or if relationship is missing. For the analysis of adverse events, the relationship to the study

	Title: Statistical Analysis Plan
	Project #: IG1002 AMBAR
	Version: Final 1.0 Effective Date: 31July2018
	Protocol Version: Version 5.0 Effective Date: Feb2018

procedure will be used as given in the CRF, regardless of whether or not the adverse event has an onset within 72 hours after the end of the last plasma exchange.

The adverse events will be summarized as follows:

- All AEs by SOC and PT
- All AEs by SOC, PT, and severity
- All AEs by SOC, PT, and causality with product
- Related AEs by SOC and PT
- Related AEs by SOC, PT, and severity
- Related AEs by SOC, PT, and relationship (product, procedure, product + procedure)
- Related AEs by SOC, PT, and product (albumin 5%, albumin 20%, Flebogamma DIF 5%)
- All SAEs by SOC and PT
- Related SAEs by SOC and PT
- SAEs with a fatal outcome by SOC and PT

The relationship to the product will be derived from the most recent plasma exchange.

For AEs which are on the date of the plasma exchange, it is assumed that the AE is during/post exchange, i.e. the AE will be associated to this PE. For the 3 active treatment groups, the derivation of the product will be as follows:

- For FPE1 to FPE6, the product is albumin 5%

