9.1.5 Analyses for Safety

All analysis of safety will be descriptive statistics. For laboratory values, summary statistics for the actual value and for the change from baseline will be provided. Adverse events will be summarized by frequency counts and percentages.

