9.2.3 Safety Analyses

All safety analyses are descriptive with no inferential statistics. Descriptions of the safety end points and their proposed analysis can be found in Section 7.2.

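### The protocol promises a comparison of adverse drug reactions with control; the SAP plans by-arm descriptive tables only, with no between-group estimate, interval or pooled active group for safety

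*SAP*

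**What the plan says.** Protocol 10.3 has two parts. It bases tolerability on description, then adds: "In addition, a comparison of Adverse Drug Reactions between the treatment and the control groups will be performed". It names no statistic, test or interval for that comparison.

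SAP 7.2 repeats the first part, "The analysis of tolerability will be based on description of the safety variables according to their nature", and moves straight to event coding; the comparison sentence is absent. SAP 9.1.5 states "All analysis of safety will be descriptive statistics", and SAP 9.2.3 states "All safety analyses are descriptive with no inferential statistics".

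On layout, SAP 7.2 says "Summaries will be presented by treatment group and overall unless otherwise noted". The SAP pools the three active arms for efficacy (7.1) and for some baseline tables (section 6: "The 3 combined active treatment groups will also be presented for the patient disposition, demographics and the medical history"). It states no pooled active group for safety.

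The primary safety criterion (SAP 7.2 and 7.2.1) is the percentage of plasma exchanges, including the albumin or IVIG infusion, that are followed by at least one related adverse event. SAP 7.2.1 limits the events to those starting within 72 hours.

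**The concern.** A stated secondary objective (Protocol section 2, SAP 2.2) is to determine whether plasma exchange with albumin and IVIG is safe. Patients aged 55 to 85 followed for 14 months will have background events, and the sham arm is the trial's own reference for separating those from harm due to the procedure or product. The protocol's added sentence appears to call for that contrast. A final report built from the SAP would show percentages by arm without a difference or its uncertainty, for any safety outcome including the primary criterion. Readers could not tell from it whether a similar-looking pair of percentages reflects real similarity or too few patients to see a difference.

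**Working it through.** The plan gives no figure on this point to reproduce. The check is a comparison of texts, followed by an illustration of what the missing intervals would show.

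**Texts side by side**

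- Protocol 10.3: description plus a comparison with control. SAP 7.2: description only. No reason for the change is given.
- SAP 7.2 to 7.2.8, 9.1.5 and 9.2.3 name no between-arm difference, ratio or interval for safety. The overall column in SAP 7.2 mixes control with active patients, so it does not stand in for a combined active group.
- SAP 7.2.2 derives the product for active arms only ("For the 3 active treatment groups, the derivation of the product will be as follows"). The by-product analysis has as its denominator the exchanges performed with that product, so sham sessions do not enter it.
- The SAP does not say whether a sham session counts as an exchange for the primary safety criterion. SAP 2.1 notes that Version 1 had no sham treatment.
- Causality: Protocol 3.4 lists patients, caregivers and raters as blind, and does not list the person who assigns causality. The serious adverse event form in Appendix 4 records the relationship to study drug (box 13) and the treatment arm, sham included (box 18), on the same form.

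**Per-patient precision**

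Inputs: 364 patients at 1:1:1:1 give 364/4 = 91 per arm and 3 × 91 = 273 pooled active. The documents give no sham-arm event rate, so all risks here are assumptions. Simple Wald interval: d ± 1.96 × √[p₁(1−p₁)/n₁ + p₀(1−p₀)/n₀].

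| Assumed risks, active v control | n | Difference (points) | 95% CI |
|---|---|---|---|
| Adverse reaction, 20% v 10% | 273 v 91 | 10 | 2.2 to 17.8 |
| Adverse reaction, 20% v 10% | 91 v 91 | 10 | −0.3 to 20.3 |
| Serious event, 10% v 5% | 273 v 91 | 5 | −0.7 to 10.7 |
| Serious event, 10% v 5% | 91 v 91 | 5 | −2.6 to 12.6 |

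For example, row 4: √(0.10×0.90/91 + 0.05×0.95/91) = 0.0389; × 1.96 = 0.076.

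Over control risks of 10% to 40% and excesses of 10 to 20 points, the half-width is about 10 to 14 points at 91 v 91 and about 8 to 12 points at 273 v 91.

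**Per-session precision**

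A patient can contribute 6 + 12 = 18 sessions, so an arm has at most 18 × 91 = 1,638. Sessions within a patient are correlated; with intra-patient correlation ρ the variance is multiplied by 1 + 17ρ. For the active rate I take 7%, the lower of the two figures in the review of plasma exchange in Guillain-Barré syndrome that the protocol cites (5.2.2.7), where the unit is not stated. The control rate of 3% and ρ are assumptions. For one arm v control, difference 4 points:

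| ρ | 1 + 17ρ | Half-width (points) | 95% CI |
|---|---|---|---|
| 0 | 1.0 | 1.5 | 2.5 to 5.5 |
| 0.1 | 2.7 | 2.4 | 1.6 to 6.4 |
| 0.3 | 6.1 | 3.7 | 0.3 to 7.7 |

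An interval that ignored clustering would be too narrow by a factor of √2.7 ≈ 1.6 to √6.1 ≈ 2.5.

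**The case against.** The plan does use the control arm for safety. SAP 5.3 puts controls in the safety set ("Control group subjects will also be included (without the plasma exchange) if they attended at least 1 of the 6 intensive treatment phase visits"), and the event tables in SAP 7.2.2 will show their percentages next to each active arm. Protocol 12.4 has the data monitoring committee compare event rates between each arm and control. A reader might infer from the missing sentence that the sham arm goes unused, or that a clear excess would stay hidden. The documents do not support either: 20% and 10% in adjacent columns disclose a 10-point excess.

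A reader might also infer that the SAP breaks a promise of inferential analysis. That is not supported either. Protocol 10.3 names no test or interval, the 5% level and 95% intervals in Protocol 10.2.1 belong to efficacy, and the protocol synopsis itself carries only the descriptive sentence. Side-by-side tables are arguably a comparison. The study is also sized for efficacy alone and states no safety margin.

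These points remove the stronger readings. They do not supply the size of the excess with its precision, a combined active safety group, or a defined control value for the primary safety criterion. Committee review during the trial is oversight and does not replace the final analysis.

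**Conclusion.** The point holds as a gap in specification and reporting. The protocol calls for a comparison beyond description, and the SAP neither defines one nor explains its omission. What is lost is the precision of any excess and a statement of what excess is excluded. On the assumed rates, a 5-point excess in serious events would leave excesses up to about 11 points (pooled) or 13 points (single arm) unexcluded, and the report would not say so. Those figures rest on assumed risks, 91 randomised patients per arm rather than the realised safety set, and Wald intervals; they show scale only. The efficacy analyses are not affected. The change is worth making because it carries out a written commitment at almost no cost.

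**What to change.** Amend SAP 7.2, 9.1.5 and 9.2.3 as follows.

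1. For each active arm minus control, and for the combined active group minus control, report the difference in the percentage of patients with, in this order: at least one treatment-emergent adverse event of any cause; at least one serious adverse event; at least one adverse reaction. Give each a two-sided 95% confidence interval (Newcombe or Miettinen-Nurminen) and no p-value. Any-cause outcomes come first because the person assigning causality is not stated to be blind.
2. Define adverse reaction by the relatedness rule in SAP 7.2.2, which counts unlikely and missing as related. State where the definite category falls, since the rule's list does not name it.
3. For the per-exchange primary safety criterion, report the difference with an interval clustered by patient. Use sham sessions as the control denominator. Leave Version 1 controls out of this comparison, because they had no sham sessions, and say whether Version 1 active sessions stay in. State how missing relationship is treated, because the per-exchange analysis in SAP 7.2.2 drops it while the per-patient tables count it as related.

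If the sponsor prefers description only, the SAP should state and justify the change from Protocol 10.3.

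Cost: a few columns in tables already planned, from data already collected. The downside is that some chance differences will appear among the several intervals, which a footnote can say.
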